Short-term Efficacy of Chlorhexidine and Povidone-Iodine Mouth Rinses in Reducing Salivary SARS-CoV-2 Viral Load: A Randomized Controlled Clinical Trial

NCT04941131

June 24, 2021

[name]

1. Background and Rationale

Severe Acute Respiratory Syndrome Coronavirus 2 (SARS-CoV-2) is primarily transmitted through respiratory droplets and aerosols. Dental procedures pose a significant transmission risk due to close proximity to the oral cavity and aerosol generation. Saliva has been identified as a potential reservoir for SARS-CoV-2. Therefore, reducing viral load in saliva prior to dental treatment may reduce the risk of cross-infection.

Several antiseptic mouth rinses have been proposed as preprocedural interventions to reduce viral load in the oral cavity. This study evaluates and compares the short-term effects of chlorhexidine (in both rinse and lozenge forms) and povidone-iodine mouth rinse on salivary viral load in confirmed COVID-19 patients.

2. Objectives

Primary Objective

- To evaluate the short-term efficacy of different mouth rinses and lozenges (chlorhexidine rinse, chlorhexidine lozenges, and povidone iodine rinse) in reducing salivary SARS-CoV-2 viral load.

Secondary Objective

- To compare each intervention with saline as a control.
- To assess changes in viral load using Ct values of E and S genes via RT-PCR.

Material and methods:

3. Study Design

- This study is a **four-arm, open-label, randomized controlled clinical trial** designed to evaluate the short-term efficacy of three oral antiseptic interventions—chlorhexidine digluconate mouth rinse, chlorhexidine digluconate lozenges, and povidone-iodine (PVP-

I) mouth rinse—compared to a saline control in reducing salivary SARS-CoV-2 viral load in COVID-19-positive patients.

- **Type of Study:** Open-label, randomized controlled clinical trial
- **Study Setting:** King Fahad General Hospital and Al-Hamra Community Health Center, Jeddah, Saudi Arabia
- **Registration:** ClinicalTrials.gov (NCT04941131)
- **Ethical Approval:** Jeddah Health Affairs (#1485)

Study Design

Randomization and Blinding

- **Randomization:** Participants will be allocated using a simple 1:1:1:1 randomization schedule generated via computer-based random number sequencing.
- **Allocation Concealment:** Allocation will be performed using sealed opaque envelopes.
- **Blinding:** This is an open-label study due to the obvious physical and functional differences between interventions (rinse vs. lozenge), which preclude participant and clinician blinding. However, the **laboratory personnel and statisticians will be blinded** to group allocation.

4. Participants

Inclusion Criteria:

- Adults aged ≥ 18 years
- Positive nasopharyngeal RT-PCR for SARS-CoV-2
- Ability to provide informed consent

Exclusion Criteria:

- Known allergy to study substances (chlorhexidine or povidone-iodine)
- Pregnancy

- Prior COVID-19 treatment
- Severe oral lesions that contraindicate rinse use

5. Interventions

Participants were randomized into four arms:

1. Chlorhexidine Mouth Rinse (CHX):

10 mL undiluted solution, used for 30 seconds.

2. Chlorhexidine Lozenges (CHX Lozenges):

2 mg lozenge to dissolve slowly in the mouth.

3. Povidone Iodine Mouth Rinse (PVP-I):

10 mL undiluted solution, used for 30 seconds.

4. Control (Saline):

10 mL normal saline rinse, used for 30 seconds.

All participants were instructed to refrain from eating, drinking, or oral hygiene procedures for at least 30 minutes before the intervention.

6. Sample Collection and Laboratory Testing

- **Saliva Collection:** Passive drool technique; 3 mL of saliva collected before and after intervention (5 minutes apart).
- **Analysis Method:**

Real-time RT-PCR using LabGun COVID-19 Kit (Biosewoom, Korea).

- Targets: E gene and S gene
- Measurement: Threshold cycle (Ct) values

7. Sample Size Calculation

- **Software:** G*Power 3.1
- **Effect size:** 1.1
- **Power:** 80%
- **Alpha:** 0.05
- **Required Sample:** 15 participants per group (Total N = 60)

Sample Size Justification:

- Based on an expected moderate-to-large effect size (Cohen's $f = 0.4$), $\alpha = 0.05$, power = 0.80, and four groups:
 - **Required sample = 60 participants (15 per group)**
 - Power calculation was performed using **G*Power 3.1**.
- To account for 10% attrition, **a total of 66 participants will be recruited**.

8. Statistical Analysis

Statistical Analysis

Software:

- Data will be analyzed using **IBM SPSS Statistics version 25** and **R (v4.3 or later)** for confirmatory and exploratory analyses.

Analysis Population:

- **Intention-to-treat (ITT):** All randomized participants will be included in the primary analysis, with imputation for missing data.

Primary Outcome Analysis:

- **Primary Endpoint:**
 - Change in **Ct value** of SARS-CoV-2 E and S genes from baseline to post-intervention (ΔCt).

- **Between-Group Comparison:**
 - **One-way ANOVA** to assess differences in mean ΔCt across all four groups.
 - **Post-hoc Bonferroni test** for pairwise comparisons.
 - If assumptions of ANOVA are violated, **Kruskal–Wallis test with Dunn’s test** for post-hoc comparisons will be used.
- **Within-Group Comparison:**
 - **Paired t-test** to compare pre- and post-intervention Ct values within each group.
 - **Wilcoxon signed-rank test** will be used if normality is not met.

Assumptions and Validation:

- **Normality:** Assessed using **Shapiro-Wilk test** and QQ plots.
- **Homogeneity of variance:** Evaluated using **Levene’s test**.
- **Effect Size Reporting:** Partial η^2 for ANOVA, Cohen’s d for t-tests.

Missing Data Handling:

- For the ITT analysis, missing outcome data will be handled using **multiple imputation** (MI) under the assumption of missing at random (MAR).
- Sensitivity analyses using **last observation carried forward (LOCF)** will be conducted to assess the robustness of findings.

9. Expected Outcomes

- Povidone-iodine rinse will demonstrate the highest reduction in viral load.
- Chlorhexidine lozenges may show moderate efficacy.
- Chlorhexidine rinse may show variable outcomes.
- Control (saline) is expected to have no significant effect.

10. Ethical Considerations

- All participants provided informed written consent.
- Ethical approval was secured from local ethics board.
- All data were anonymized and securely stored.
- Participants had the right to withdraw at any time without consequences.

11. Timeline

Phase	Duration
Ethical Approval	Completed
Participant Recruitment	2 months
Data Collection	2 months
Laboratory Analysis	Concurrent
Data Analysis & Manuscript	1 month

12. Dissemination Plan

The study results will be disseminated through:

- Peer-reviewed publication
- Scientific conferences
- Institutional and ministry health updates

References

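### Change in salivary Ct is undefined when the baseline saliva does not amplify; the plan has no non-detect rule, and its only stated route is MAR imputation

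*Combined protocol and SAP*

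**What the plan says.** All references are to the combined protocol and SAP.

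- **Entry (section 4).** The infection criterion is "Positive nasopharyngeal RT-PCR for SARS-CoV-2". No inclusion or exclusion criterion mentions saliva.
- **Specimen and scale (section 6).** The outcome comes from saliva alone, sampled before and after the intervention. The measurement is "Threshold cycle (Ct) values" for the E and S genes. No detection limit is given, and no value for a sample that does not amplify.
- **Primary endpoint (section 8, Primary Outcome Analysis).** "Change in Ct value of SARS-CoV-2 E and S genes from baseline to post-intervention", compared across the four arms by one-way ANOVA.
- **Analysis population (section 8).** "All randomized participants will be included in the primary analysis, with imputation for missing data".
- **Missing data (section 8).** "missing outcome data will be handled using multiple imputation (MI) under the assumption of missing at random (MAR"); and "Sensitivity analyses using last observation carried forward (LOCF) will be conducted" as the robustness check.
- **Sample size (section 7).** 15 per group, 60 in total, raised to 66 for 10% attrition. Two effect sizes are given: 1.1 (metric not named) and Cohen's f = 0.4. Neither the 60 nor the 66 allows for undetectable saliva.

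**The concern.** Eligibility is fixed on one specimen and the endpoint on another. A nasopharyngeal-positive patient may have saliva in which one or both genes are not detected, and section 1 itself describes saliva only as a possible reservoir. Such a person has no baseline Ct, so no change can be calculated.

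The plan nevertheless keeps every randomized participant in the primary analysis and offers one tool for a change that cannot be computed: imputation under MAR. A non-detect has no Ct because the viral load is below what the assay can read, so its absence depends on the unobserved value itself. A model fitted to participants with detectable virus would give a typical change to someone with no measurable virus to reduce.

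The same gap exists after the intervention. A sample that amplifies at baseline but not afterwards may mark the strongest response. MAR imputation would draw that response toward the typical one, and LOCF would set it to zero. Post-intervention non-detection can differ by arm, so this half of the gap can bias the comparison directly.

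**Working it through.** **1. Is the endpoint defined for everyone?** ΔCt = Ct(post) − Ct(baseline), for each gene.

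| Baseline saliva | Post saliva | ΔCt | What MI under MAR would do | What LOCF would do |
|---|---|---|---|---|
| detected | detected | defined | not needed | not needed |
| not detected | either | undefined | borrow a change from detectable participants | nothing to carry |
| detected | not detected | undefined (at least cut-off minus baseline) | draw a typical change | set ΔCt = 0 |

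E and S may fall in different rows for the same participant, and the plan has no by-gene rule.

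**2. Would it arise?** The share u of baseline non-detects is not in the document, so these values are assumptions. The chance of at least one among 60 is 1 − (1 − u)^60.

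- u = 5%: 1 − 0.95^60 = 95%; expected number 60 × 0.05 = 3
- u = 10%: 1 − 0.90^60 = over 99%; expected number 6

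At u = 0 the issue does not arise.

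**3. The plan's own sample size.** Inputs from section 7: alpha 0.05 (taken as two-sided), power 80%, 15 per group.

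- *Effect size 1.1, read as Cohen's d, two-sample t-test.* Noncentrality = d × √(n/2), df = 2n − 2. At n = 14 power is 79.99%; at n = 15 the noncentrality is 1.1 × √7.5 = 3.01 and power is 82.8%. So 15 per group reproduces on this basis.
- *Cohen's f = 0.4, one-way ANOVA, four groups.* Noncentrality = N × f², df = 3 and N − 4. At N = 60 it is 60 × 0.16 = 9.6 and power is 70.9%. N = 72 gives 79.9% and N = 76 gives 82.3%. So 60 does not reproduce on this basis. That is a separate defect and is not caused by non-detects.

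**4. Evaluable numbers and power.** Evaluable = N × (1 − u), rounded to whole participants and split equally over four arms.

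| u (assumed) | Start | Evaluable | Power, d = 1.1 | Power, f = 0.4 |
|---|---|---|---|---|
| 0% | 60 | 60 | 82.8% | 70.9% |
| 10% | 66 | 59 | 82% | 70% |
| 20% | 66 | 53 | 78% | 64% |
| 30% | 66 | 46 | 71% | 57% |
| 10% | 60 | 54 | 78% | 65% |
| 20% | 60 | 48 | 73% | 59% |
| 30% | 60 | 42 | 67% | 52% |

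The rows from 66 assume no other attrition. The rows from 60 apply if the 10% attrition allowance is used up as planned.

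**The case against.** **The plan never calls a non-detect missing.** A sample that was collected, assayed and read as negative is a result. Assigning the cut-off Ct would be compatible with the text and would give a change near zero to someone negative both times. This stands. A reader might infer that the ITT imputation is certain to invent a change for a set number of participants, such as 6 / 12 / 18 of 60; the document does not support that. It supports something narrower: handling is unspecified, and the only route written down is one that does not suit a non-detect. If the analyst chose another rule after seeing the data, the primary analysis would not have been pre-specified.

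**The frequency is unknown, and 66 are recruited.** Both samples belong to one short sitting, so ordinary loss may be small, and at 10% non-detects the 66 leave about 59, essentially the planned 60. This also stands. A reader might conclude that the evaluable number must fall below 60, but that depends on a rate the document does not give. The margin was, however, set aside for attrition, and it does not cover 20 or 30%.

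**Quoting power only at f = 0.4 makes the loss look worse.** This is correct: the shortfall from 80% to 70.9% exists before any non-detect. Hence both bases are shown.

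**Restriction is not the only defensible repair.** A salivary entry criterion, a cut-off substitution or a censored-data model could also work. This is true, but one of them has to be written down in advance.

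**Conclusion.** The concern holds in a bounded form. The primary endpoint is undefined for a foreseeable kind of participant, no rule classes a non-detect, and the stated combination of ITT inclusion, MAR imputation and LOCF gives a poor answer if followed as written. This does not depend on the sample size, and even an assumed 5% share makes at least one case among 60 very likely (95%).

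The power cost is conditional on an unknown share. At d = 1.1, a 10 / 20 / 30% share changes power from 82.8% at 60 to between 78 and 82% / 73 and 78% / 67 and 71%, depending on how much of the attrition margin is left. At f = 0.4 the corresponding ranges are 65–70% / 59–64% / 52–57%, against 70.9%. These figures assume equal arms, two-sided alpha for the t-test, 1.1 read as Cohen's d, and unchanged effect sizes among evaluable participants. They do not show that the trial will be underpowered because of non-detects, and they do not show that the result will be biased in a known direction.

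**What to change.** Add a short paragraph to section 8:

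1. For each gene, define the primary analysis set as randomized participants with a detectable baseline saliva Ct for that gene. Section 6 places this sample before the intervention and section 3 has laboratory staff blinded to allocation, so the restriction does not depend on treatment.
2. State the assay cut-off that defines a non-detect. Do not impute a Ct for baseline non-detects, and report their number by arm and gene.
3. Treat post-intervention non-detects as censored at the cut-off, or assign the cut-off Ct with a sensitivity analysis. Do not use MAR imputation or LOCF for them. Keep multiple imputation for samples that were not obtained or not assayed.
4. In section 7, restate power for the expected evaluable number. To keep 60 evaluable at 10 / 20 / 30% non-detects, 60 ÷ (1 − u) gives 67 / 75 / 86 recruits; dividing also by 0.9 for the plan's attrition gives 75 / 84 / 96.

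Items 1 to 3 need SAP wording only, with no new visit, sample or assay. The small downside is a primary set smaller than all randomized and a less favourable stated power. Recruiting more to offset this is optional and would add cost.

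### Section 7's f = 0.4 gives about 71% power at N = 60 under the planned ANOVA, not 80%, and an unlabelled effect size of 1.1 is attached to the same N

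*Combined protocol and SAP*

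**What the plan says.** Section 7 supports one sample size in two ways, both credited to G*Power 3.1.

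- The opening list gives "Effect size: 1.1" with 80% power and alpha 0.05, and arrives at 15 per group, 60 in total. It names neither a metric nor a test.
- The Sample Size Justification begins "Based on an expected moderate-to-large effect size", identified as Cohen's f = 0.4, adds alpha 0.05, "power = 0.80, and four groups", and concludes "Required sample = 60 participants (15 per group"). Recruitment is then raised to 66 for 10% attrition.

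Section 8 defines the analysis that this sample must support. The between-group test is "One-way ANOVA to assess differences in mean" change in Ct over the four arms, followed by "Post-hoc Bonferroni test for pairwise comparisons". The primary endpoint is the change in Ct "of SARS-CoV-2 E and S genes from baseline to post-intervention", with no rule for combining the two genes. Section 2 lists as a secondary objective "To compare each intervention with saline as a control".

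**The concern.** The justification fixes every input that a one-way ANOVA power calculation needs, so its result can be checked directly, and 60 is not the number those inputs produce. The second effect size makes this harder to resolve. An effect of 1.1 cannot be on the same scale as f = 0.4 and lead to the same N, and nothing says what it measures.

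The power statement is what a reader uses to interpret a non-significant result. If f = 0.4 is the design effect, the chance of missing it is about 29% per gene at 60 complete outcomes, not 20%. If 1.1 is the design effect and means Cohen's d, the stated 80% belongs to a comparison that the plan does not make between arms. Type I error and the treatment estimates are not affected.

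**Working it through.** **Inputs.** From Section 7: f = 0.4, alpha = 0.05, target power 0.80, k = 4 groups, N = 60 (66 recruited), and a separate effect size of 1.1. From Section 8: one-way ANOVA on change in Ct, then Bonferroni pairwise tests.

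**1. The justification as written.** ANOVA power is P(F' > F_crit), where F' is noncentral F with 3 and N − 4 degrees of freedom and noncentrality λ = f²N.

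At N = 60: λ = 0.16 × 60 = 9.6, df = (3, 56), F_crit = 2.77, power = 0.709.

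| N | λ | Power |
|---|---|---|
| 60 | 9.60 | 0.709 |
| 66 | 10.56 | 0.757 |
| 72 | 11.52 | 0.799 |
| 73 | 11.68 | 0.805 |
| 76 (19 per arm) | 12.16 | 0.823 |

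The stated 60 is not reproduced. The smallest N reaching 0.80 is 73, or 76 in equal arms. Solving for f at 80% power gives 0.44 at N = 60 and 0.42 at N = 66.

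**2. Variants that might have produced 60.** At N = 60 and f = 0.4:

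- chi-square large-sample approximation: 0.742
- ANCOVA degrees of freedom (55): 0.708
- three groups: 0.776
- alpha 0.10: 0.812

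Only alpha 0.10 reaches 80%, and it contradicts the stated alpha. Repeated-measures models can also exceed 80%, but they are not the planned test and need a correlation that the documents do not give. With two measures and an assumed correlation of 0.5, the between-groups version needs N = 56, not 60.

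**3. Where 15 per group may come from.** Assume that 1.1 is Cohen's d. For a two-sided two-sample t-test at unadjusted alpha 0.05, the noncentrality is d√(n/2).

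- n = 14: 1.1 × √7 = 2.91, power 0.7999
- n = 15: 1.1 × √7.5 = 3.01, power 0.828

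The smallest n with power of at least 0.80 is 15, which matches the plan. Read as Cohen's f, 1.1 would give power above 99.9% at N = 60, so that reading does not explain the figure.

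**4. What d = 1.1 would mean for the tests actually planned.** For pairwise tests at 15 per arm, the ranges run from separate df (28) to pooled df (56):

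| Bonferroni family | Power at d = 1.1 | d detectable at 80% | n per arm needed for d = 1.1 |
|---|---|---|---|
| 3 comparisons with saline | 0.68 to 0.71 | 1.21 to 1.25 | 19 |
| all 6 pairs | 0.57 to 0.61 | 1.31 to 1.36 | 21 to 22 |

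For the ANOVA at N = 60, f is the SD of the four arm means in within-group SD units, so it depends on how the means are arranged across a range of 1.1:

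| Pattern of means | f | Power |
|---|---|---|
| one arm at each extreme, two midway | 1.1 × √(1/8) = 0.39 | 0.68 |
| equally spaced | (1.1/2) × √(5/9) = 0.41 | 0.73 |
| one arm differs from the other three | 1.1 × √3/4 = 0.48 | 0.86 |
| two arms at each end | 1.1/2 = 0.55 | 0.95 |

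The documents specify no pattern, so d = 1.1 alone does not fix the power of the ANOVA.

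**5. Two genes.** The 0.709 applies to one gene tested at 0.05. As an illustration, 20,000 trials were simulated per correlation, with one arm differing, f = 0.4 for each gene, and assumed between-gene correlations of 0.5 to 0.95. At least one gene was significant in 0.86 down to 0.76 of trials, and both in 0.57 up to 0.66. If alpha were split to 0.025 per gene, power per gene at N = 60 would be 0.600.

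**The case against.** The strongest reply is that the primary analysis is intention-to-treat with multiple imputation, so it contains all 66 randomised participants. On that view power lies between about 0.71 (10% of outcomes lost, nothing recovered by imputation) and 0.76 (no loss), and the shortfall is 4 to 9 percentage points rather than a flat 9. That is fair as a range. It does not restore 80%, and the plan itself presents 60, not 66, as the number that delivers the stated power.

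Second, the Cohen's d reading of 1.1 is inferred, not documented. This stands. The match to 15 per group makes it plausible, but the 14-per-group power of 0.7999 shows how fine the margin is. What needs no assumption is that 1.1 has no metric or test and sits beside f = 0.4 for the same N. Nor does it help to argue that the two figures agree: equally spaced means spanning d = 1.1 do give f = 0.41, but ANOVA power is then 0.73.

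Third, the pairwise tests are post hoc and the plan never claims 80% power for them, while the two-gene figures use assumed correlations. Both are illustrative here, and the main result does not depend on them.

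Finally, some ways of arranging the arm means would give the trial adequate power, and the remedy changes nothing in its conduct. Both are true, but the design statement is still wrong on its own inputs.

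**Conclusion.** The concern holds. With f = 0.4, alpha 0.05 and four groups, the planned ANOVA has power of 0.71 per gene at 60 complete outcomes and at most 0.76 at 66, against a stated 0.80. The sample is 13 short of the 73 required (16 short of 76 in equal arms). This rests only on inputs printed in Section 7 and the test named in Section 8; the words per gene reflect a separate test of E and S, each at 0.05, because the plan gives no other rule.

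The unlabelled 1.1 is a second, unreconciled basis for the same N. Every figure derived from it above is conditional on its being Cohen's d. The error lies in the stated power, not in the validity of the test, but it is the trial's central design claim and should be corrected.

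**What to change.** Keep N and correct the text of Section 7. Suggested content: 60 participants with complete outcomes give about 71% power per gene for f = 0.4 in the four-group one-way ANOVA at alpha 0.05; 80% power corresponds to f of about 0.44. It would help to add that power is about 76% if all 66 recruits have complete outcomes.

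Keep one effect size, and name its metric and the test it belongs to. If 1.1 is retained as Cohen's d for pairwise comparisons, state the power under the planned Bonferroni correction and say which comparisons are meant: about 0.68 to 0.71 for the three comparisons with saline, or 0.57 to 0.61 for all six pairs.

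The cost is protocol wording only. Sample size, arms, test and alpha are unchanged; the drawback is a less favourable stated power.

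### Section 7 sets the recruitment target by adding 10% to 60, so 66 recruits allow for 9.1% attrition rather than the stated 10% (a minor arithmetic error)

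*Combined protocol and SAP*

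**What the plan says.** The Sample Size Justification in Section 7 of the combined protocol and SAP gives the requirement as "Required sample = 60 participants (15 per group" and follows it with the allowance: "To account for 10% attrition, a total of 66 participants will be recruited". It does not show how 66 was obtained or how 66 is divided over the arms.

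Three other passages bear on the point:

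- Section 3, Randomization and Blinding: "Participants will be allocated using a simple 1:1:1:1 randomization schedule". No blocking or other restriction on arm sizes is described.
- Section 8, Analysis Population: "All randomized participants will be included in the primary analysis, with imputation for missing data".
- Section 6: "3 mL of saliva collected before and after intervention (5 minutes apart". The outcome therefore needs only two samples from one short session.

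**The concern.** An attrition allowance is meant to leave the required number after the assumed share of recruits has been lost. Here the 10% appears to have been taken of the required 60 instead of the number recruited. If so, the recruitment target falls short of the stated requirement under the plan's own loss assumption.

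What is at stake is mainly the internal consistency of Section 7. The plan says that 66 accounts for 10% attrition, and on average it does not quite do so. The same formula, applied to a larger base or a higher attrition rate, would produce a larger shortfall.

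**Working it through.** **Inputs, all from Section 7:** required N = 60 (15 per group); attrition d = 10%; recruitment target = 66.

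**1. Reproduce the plan's figure.** N x (1 + d) = 60 x 1.10 = 66 exactly. The alternative, N/(1 - d) = 60/0.90 = 66.67, rounds up to 67 and cannot round up to 66. The stated figure therefore matches the additive formula.

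**2. Apply the stated attrition to the stated target.**

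| Recruited | Expected completers at 10% loss | Chance of at least 60 completers |
|---|---|---|
| 66 | 66 x 0.90 = 59.4 | 0.51 |
| 67 | 67 x 0.90 = 60.3 | 0.65 |
| 68 | 68 x 0.90 = 61.2 | 0.76 |

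The last column is a binomial tail and assumes that participants are lost independently, each with probability 0.10. That assumption is added here and is not in the plan.

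**3. Find the attrition that 66 can absorb.** 66 - 60 = 6 losses, and 6/66 = 9.1%.

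**4. Size the effect on power.** Section 7 states two effect sizes, "Effect size: 1.1" with no metric named, and Cohen's f = 0.4 with four groups. Both were checked at two-sided alpha 0.05 for the t-test and alpha 0.05 for the F-test.

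- One-way ANOVA, four groups, f = 0.4, noncentrality f² x N: power is 0.709 at N = 60 and 0.700 at N = 59. The difference is 0.009, under one percentage point.
- Two-group t-test, reading 1.1 as Cohen's d: power is 0.828 at 15 per group and 0.7999 at 14 per group. Even a full participant fewer in both groups leaves power at 80% after rounding.

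**5. Separate this from the base N.** On the ANOVA basis, 60 gives 0.709, and 19 per group (76 in total) is the smallest equal-arm design that reaches 80%. Recruiting 67 or 68 to retain about 60 would leave that power where it is. Even with nobody lost, 68 gives 0.772.

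**6. See what the formula would do to another base.** Taking 76 only as an illustration, 76 x 1.10 = 83.6, so 84, whereas 76/0.90 = 84.4, so 85. The method carries the same bias to any base.

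**The case against.** The strongest reply is that the gap is finer than the assumption behind it. Ten percent is a round planning figure with no stated derivation, and 9.1% is close to it. The two saliva samples are 5 minutes apart, so losses may well be below 10%. All randomized participants enter the primary analysis with imputation. The figure of 59 completers is an expectation: even at a 10% loss rate, 66 recruits are about as likely as not to leave at least 60. Most of this stands, and it is why the point is minor. It does not make 66 the right target for 10%. Imputation keeps people in the analysis set but does not restore their lost outcomes, and a belief that attrition is lower would be a reason to state a lower rate.

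A reader might infer something stronger: that 66, not being divisible by four, cannot give four arms that each keep 15. The documents do not support this. Arms of 16, 16, 17 and 17 that lose 1, 1, 2 and 2 participants keep exactly 15 each, with six losses in all. Nor can per-arm probabilities be based on fixed arm sizes, because simple randomization, as Section 3 describes it, does not fix them. Simulating unrestricted allocation with independent 10% loss, every arm keeps at least 15 in about 0.8% of trials with 66 recruits and about 2.4% with 68. Divisibility by four therefore secures little, and the plan promises no probability of 15 completers in every arm.

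**Conclusion.** The point holds as a minor arithmetic error. Section 7 multiplied 60 by 1.10 where it should have divided by 0.90. The target of 66 is one short of 67, leaves 59.4 expected completers against 60 at 10% loss, and covers 9.1% attrition. The consequence for the four-group ANOVA at f = 0.4 is under one percentage point of power.

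This rests on reading the 60 as a number of completers, which is the natural meaning of adding an attrition allowance to it, and on 10% applying to those recruited.

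A reader might also infer that moving to 67 or 68 would make the trial adequately powered. It would not do so at f = 0.4, because the base of 60 does not reach 80% there. That is a separate question, which this correction neither raises nor resolves.

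**What to change.** Restate the sentence in Section 7 and leave enrolment unchanged. Suggested wording: *66 participants will be recruited, which allows for 6 losses (9%); at 10% attrition about 59 completers are expected.* If the base sample size is revised for any other reason, compute the recruitment target as N/(1 - attrition), round up, and show the formula.

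The cost is one line of text. It adds no participants and changes no analysis. The stated allowance becomes slightly less favourable, at 9% instead of 10%.

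### The plan makes changes in both E and S primary but has no rule for combining them, so the overall between-arm ANOVA exceeds 5% false positives if either gene may carry the conclusion

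*Combined protocol and SAP*

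**What the plan says.** Section 6 lists two PCR targets ("Targets: E gene and S gene"), each read as a Ct value. In section 8 the primary endpoint is "Change in Ct value of SARS-CoV-2 E and S genes from baseline to post-intervention (ΔCt". The between-group test is "One-way ANOVA to assess differences in mean ΔCt across all four groups", followed by "Post-hoc Bonferroni test for pairwise comparisons". Kruskal–Wallis with Dunn's test is the fallback.

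Section 2 places the same measurements under the secondary objective: "To assess changes in viral load using Ct values of E and S genes via RT-PCR". Neither section names a lead gene. The only alpha is the 0.05 in section 7, with no split between genes.

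**The concern.** A one-way ANOVA takes one outcome per participant, and the plan supplies two. A natural way to follow the text is to run the ANOVA once per gene. The plan does not then say whether one significant gene is enough or both are needed. Bonferroni is named for pairs of arms, so it does not cover the two genes.

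Two things are at stake. If either gene suffices at 0.05, the overall statement that some arm differs has more than a 5% chance of being false. If the genes disagree, the plan defines no conclusion, and the deciding gene or rule could be chosen after the data are seen.

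This point covers the between-arm comparison only. The within-arm paired tests are a separate matter.

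**Working it through.** **Inputs from the documents.** Four arms, 15 per arm, N = 60, alpha 0.05, power 80%, Cohen's f = 0.4 for four groups (section 7); two genes (sections 6 and 8). The ANOVA therefore has 3 and 56 degrees of freedom.

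**Assumptions.** The within-arm correlation ρ between the two genes' changes is not given, so it is shown at 0.5, 0.8, 0.9 and 0.95. Changes are taken as bivariate normal with equal variances. Bonferroni is taken over all pairs of four arms, 4 × 3 / 2 = 6.

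**The plan's own figure.** Fifteen per group reproduces for a two-sided two-sample t-test if the unlabelled "Effect size: 1.1" is read as Cohen's d (power 82.8%). For the four-group ANOVA at f = 0.4, the noncentrality is 60 × 0.4² = 9.6 and the power is 0.709, not 0.80. That gap is a separate sample-size issue. Here 0.709 serves only as the single-gene benchmark.

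**False-positive rates with no true effect, each gene at 0.05, either sufficient.** If the genes are independent, the ANOVA rate is 1 − 0.95² = 0.0975. For correlated genes, by simulation (separate runs agree to about 0.1 percentage point):

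| ρ | 0.5 | 0.8 | 0.9 | 0.95 |
|---|---|---|---|---|
| ANOVA significant in either gene | 9.2% | 8.0% | 7.2% | 6.6% |
| Any Bonferroni pair, either gene, only after that gene's ANOVA | 7.1% | 6.1% | 5.5% | 5.1% |
| Any Bonferroni pair, either gene, no such gate | 7.6% | 6.6% | 5.9% | 5.5% |
| Any product-versus-saline pair, either gene, no gate | 4.3% | 3.7% | 3.4% | 3.1% |
| One ANOVA on the mean of the two genes | 5.0% | 5.0% | 5.0% | 5.0% |

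The plan does not say whether the pairwise tests wait for a significant ANOVA, so both versions are shown.

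**Bound for comparisons with saline.** Three of the six pairs involve saline, each tested at 0.05/6. Over two genes the error is at most 2 × 3 × 0.05/6 = 0.05, whatever the correlation.

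**Disagreement and power, true f = 0.4 in both genes:**

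| ρ | 0.5 | 0.8 | 0.9 | 0.95 |
|---|---|---|---|---|
| Exactly one gene significant | 30% | 19% | 13% | 9% |
| Both significant | 0.56 | 0.61 | 0.64 | 0.66 |
| Mean of the two genes significant | 0.84 | 0.76 | 0.73 | 0.72 |

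The last row uses noncentral F. With unit variances the mean has variance (1 + ρ)/2, so its effect size is the average f divided by √((1 + ρ)/2). At ρ = 0.8 the noncentrality is 9.6/0.9 = 10.67 and the power is 0.76.

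**Unequal effects, f = 0.4 and 0.3, same pattern across arms.** The average f is 0.35. At ρ = 0.8 the noncentrality is 60 × 0.35²/0.9 = 8.17 and the power is 0.63. Across the four correlations the mean has power 0.72 / 0.63 / 0.60 / 0.59, against 0.71 for the stronger gene alone and 0.44 for the weaker.

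**The case against.** The strongest reply is that the plan never says either gene suffices. It has one primary endpoint and one ANOVA. If both genes must be significant, or one leads, or they are combined, nothing is inflated. This stands in part: the excess is conditional. But the text picks none of these rules, so the lack of a defined conclusion when the genes disagree remains under separate testing.

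Second, both genes come from the same saliva sample and the same kit, so a high correlation is plausible and the upper figures may not apply. That is fair, though the documents do not establish it. The ANOVA rate exceeds 5% at any correlation below 1.

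Third, the claims readers will care about most are each product against saline. A reader might infer that these are inflated too. Under six-pair Bonferroni they are not, by the bound above. That bound holds for the ANOVA branch with all six pairs. It does not cover product-versus-product claims, or Dunn's test, for which no adjustment is named.

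Fourth, testing each gene at 0.025 would also control the error (at most 4.94%) and keep both genes primary. That is correct, but at f = 0.4 it lowers each gene's ANOVA power from 70.9% to 60.0%.

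**Conclusion.** The point holds as a gap in the decision rule. Under an either-gene reading at 0.05 each, the overall between-arm ANOVA has a false-positive rate of about 6.6% to 9.2% for assumed correlations of 0.95 to 0.5. The full set of pairwise claims reaches about 5.1% to 7.1% if gated by the ANOVA and 5.5% to 7.6% if not.

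A reader might infer that the trial as planned runs at nearly 10%, or that a finding for any one product is unreliable on this ground. The documents support neither. They adopt no either-gene rule, 9.75% requires independent genes, and comparisons with saline stay within 5% under six-pair Bonferroni. The excess concerns the overall statement that some arm differs and, to a lesser degree, the full set of pairwise claims.

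The undefined outcome when the genes disagree is at least as important: about 9% to 30% of trials if f is truly 0.4 in both genes. All these sizes except the saline bound and the 9.75% depend on the assumed correlation and the normal model.

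**What to change.** In section 8, define the single primary outcome as each participant's mean of the E and S changes in Ct. Test it once at 0.05 by ANOVA, or by Kruskal–Wallis if the fallback applies, and report each gene separately as supportive. Naming one gene as primary and the other as secondary is an acceptable alternative. Align the secondary objective in section 2 with the choice. If results by arm have already been seen, report both genes and the mean, and label the rule as post hoc.

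The cost is text only, with no new data. Gene-specific results lose primary status. With equal effects and variances the mean has at least single-gene power (0.72 to 0.84 against 0.71). If the effects differ and the correlation is high, it has less power than the stronger gene: 0.59 to 0.63 against 0.71 for f = 0.4 and 0.3 at correlations of 0.95 to 0.8, with equal variances assumed. The documents do not show which gene would be the stronger. The change controls error for the overall between-arm test only.
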